## *Test Subject Recruitment*

ICR has been conducting repellent studies for over twenty years. During this time ICR has amassed a large list of potential study subjects. These subjects also refer friends and colleagues to us. When a repellent study date has been established, ICR will contact potential study subjects by telephone and briefly discuss the study, the date of the study, and location if different than ICR. Any study specific inclusion/exclusion requirements will also be mentioned at this time. When the number of interested subjects required for a particular study has been met, ICR will stop recruitment.

ICR uses the following initial telephone script to recruit test subjects:

"ICR will be conducting a repellent project on these dates, (Month, Day(s), Year), at (exact study site) would you be available to participate in this study?"

If the potential test subject is available, the inclusion/exclusion criteria will be discussed in detail and verified whether the subject qualifies to participate. The ICD will also be discussed with the test subject at this time. In addition, ICR will mail a copy of the ICD to each interested test subject for their review. They will be instructed to contact the P.I. to verify receipt of the ICD and to ask any ICD or study related questions they may have.

The P.I. will contact all interested subjects by phone several days after receipt of the ICD to fully explain the ICD with them. All contacted people that show interest will be offered the opportunity to come to ICR to go through the consent process in person.

ICR has been fully compliant with 40 CFR 26.1125 in obtaining written approval for all repellent studies from an independent Institutional Review Board

In the event that an interested subject declines to sign an informed consent document, they will not be permitted to participate in the study.

There is no coercion for any subject to participate. The inclusion/exclusion criteria are clear, the payment is clear, the subjects are informed of the conditions they will likely encounter and what is expected of them. Each consenting test subject will be informed that they may drop out of the study at any time. Further, they may leave as soon as practical after early withdrawal from the test.

## **METHODS**

### *Experimental Design*

This is a subject-blinded study. The delineated areas on the arms of subjects will be treated and used as test areas. Only arms are being treated in this study, since arms are quite easy to monitor for mosquito activity. Therefore there will be twelve test arms for each treatment. Each test

subject will have one arm treated with one of the two test products and the other arm will be treated with the other test product.

*Test location:*

This test will be conducted in the insectary at ICR. The insectary is maintained at 70% RH  $\pm$  15% RH and 70° F  $\pm$  15°F.

*Dose*

The Standard application rate of 1.67 mg/cm^2 for this study. This is the dose currently recommended in the EPA guidelines for mosquito efficacy testing and the dose that was used when the efficacy field tests were conducted on these two EPA registered products.

*Blinding of the Study*

The test articles will be coded as "A" and "B". During the test these codes will be the only test article designation referred to or that the test subjects will see. The Study Director and members of the ICR staff will know the actual test articles, but will refrain from such identifications in the presence of test subjects.

*Treatment Groups*

There will be two groups: a treated group of twelve (two more than required to allow for drop outs) subjects whose arms will be treated, and one untreated (control) test subject whose arms will be untreated. Subjects will be given a subject number. They will be assigned to the groups by lottery selection of the subject number.

*Personnel preparation*

All test subjects will complete and will sign an "Informed Consent Document" prior to acceptance as a test participant.

Females will be required to perform an over the counter pregnancy test that will be supplied by ICR. They will do this the morning of the test. The results will be verified by a female ICR staff member. They may not participate if they are pregnant or breastfeeding. The results of this pregnancy test will be kept confidential and will not be disclosed to anyone other than the test subject and the P. I.

All test subjects will wash their arms with unscented Neutrogena® soap. The test subject's arms will then be measured in the following manner for the demarcation of the 250 cm^2 test area:

*For Arms:*

The subject's elbow will be placed on a flat rigid surface with the forearm held perpendicular to that surface. A mark will be made on the upper forearm 3" from the flat surface. A second mark will be made on the lower forearm at a point just below the wrist bone. The circumference of the

arm will be measured at each of these points. The average of the two circumferences will be calculated. This represents the approximate circumference at the center point between the two marks. A third mark will be made at the center point between the two marks. The average circumference will be divided into  $250\text{cm}^2$ , the total exposed surface area required for the test. This will yield the length of arm required to be exposed. The end points of this length of exposure area will be marked on the forearm so that each end point is equidistant from the center point. The endpoint measurements from the center point will be recorded so that they may be duplicated in the laboratory. The distance from the tip of the little finger to the center point will be measured and also recorded so that the center point may be duplicated at another time.

The above mentioned measurements will be recorded on a repellent measurement form. If a test subject has been previously measured, the existing measurements will be used.

The test subjects and the control subject will have  $250\text{ cm}^2$  areas delineated around their forearms and these arms will be prepared for treatment. The skin above and below the target area will be protected with elastic bandages and or Velcro® straps held in place with Elastikon® tape. Arms will be protected by shirt sleeves. Latex or vinyl gloves will be given to the subjects to protect their hands. The control test subject will be randomly selected by flipping a coin.

#### *Determination of Attractancy to Mosquitoes*

Test subjects will then be taken to the insectary. They will then place their right forearm into their test cage and the number of mosquitoes landing on their arms will be counted. The required landings will be at least 5 mosquitoes in 60 seconds to qualify a subject as being attractive to the mosquitoes. Volunteers will repeat the qualifying exposure as above using the left arm. The procedure will be repeated if the subject fails to qualify. If a subject again fails to qualify after repeated exposure, that subject may be replaced.

After qualification the test subjects will return to the laboratory for the application of the test repellent.

#### *Treatment Application*

The repellents will be coded as "A" or "B", and each arm will be labeled on the protective wrap with the code corresponding to the repellent applied. Each test subject will be treated on the right arm with repellent "A" and on their left arm with repellent "B".

The test articles will be applied to the test subjects using a syringe (minus needle). The amount of test article applied will be determined in the dose range finding. The hands will be protected with gloves. The control subject will receive no treatment.

Subjects will be treated in pairs. Both members of a pair will be treated with one test article and then they will be treated with the other test sample. The time of treatment will be the time when

the application of the second test article begins. This time will represent the starting time used for calculation of the protection times afforded by the test samples.

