### ***STUDY OVERVIEW***

- *ICR will randomly recruit from our database of test subjects.*
- *During the recruitment process, potential test subjects will have an ICD mailed to them. They will be instructed to contact the P.I. with any ICD or study related questions.*
- *When 13 subjects have committed, recruitment will cease.*
- *Randomization and selection of test, control, and alternate test subjects will be done prior to the test initiation.*
- *All test subjects will meet at the ICR laboratory on the designated test day.*
  - *All females test subjects will take an OTC pregnancy test.*
  - *The pregnancy tests will be read by a female ICR staff member to verify that no pregnant test subjects are present.*
  - *At this meeting unscented soap will be provided to each test subject.*
  - *The study parameters will be explained to everyone.*
  - *Any subjects found to be ineligible for any reason or who decline to participate will be allowed to leave at this time. They will be compensated for the time used at the hourly rate.*
  - *Treated and control test subjects will be identified.*
  - *Treated and control subjects will wash their arms.*

- *ICR staff will measure, and establish the treatment area and untreated control area on test subjects' arms.*
- *Treatment and control areas will be bandaged and taped.*
- *Test subjects will proceed to the insectary to be tested for attractancy to mosquitoes. When completed the test subjects will return to the laboratory for treatment.*
- *Test articles will be applied to the test subjects.*
- *All test subjects return to the insectary for repellent testing.*
- *ICR staff verifies adequate mosquito activity using the control subject.*
- *Exposure begins for the treated test subjects.*
- *Treatment exposure ends either through breakdown or end of study duration*
- *ICR staff helps subjects remove bandages, clean off repellent and treat bites.*

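### Product A is always on the right arm and B always on the left, so any right/left difference cannot be separated from product; a balanced random list would prevent this at little cost

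*Protocol*

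**What the plan says.** Experimental Design sets up a within-subject comparison: each "subject will have one arm treated with one of the two test products" and the other arm with the other product. It adds: "Therefore there will be twelve test arms for each treatment". No side is named there. Treatment Application then fixes it: "Each test subject will be treated on the right arm with repellent" A, and on the left arm with B. The two sections are compatible; the second completes the first.

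The chance procedures in the Protocol concern people, not arms. The Study Overview says: "Randomization and selection of test, control, and alternate test subjects will be done prior to the test initiation". Treatment Groups says of the treated and control groups: "They will be assigned to the groups by lottery selection of the subject number". Nothing assigns product to arm by chance, no reason is given for fixing the side, and Amendments 1 to 8 leave the rule unchanged.

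The Objective is the mean protection time of the test articles. Data Analysis describes the proportion protected at each half hour, a Cochran Q test over time, follow-up exact tests against baseline, and descriptive statistics of time to failure. No test of A against B appears.

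**The concern.** Using both arms of the same person removes differences between people. It does not remove differences between right and left arms, and a fixed side loads all of any such difference onto one product. A plausible source is greater use of, or abrasion to, the dominant arm between exposures over 8 hours. The Protocol itself recognises abrasion as a threat: in Testing, staff are to keep arms from rubbing on the cage sleeve.

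The study supports an added label claim for each of two registered products (Study Rationale). Each product's protection time and half-hourly proportions would describe that product on that arm. Because both sets come from the same people on the same day, readers are also likely to set them side by side, even though no such test is planned. More subjects would not reduce this kind of error.

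**Working it through.** **Inputs.**
- A on the right and B on the left for every subject: Treatment Application.
- Twelve treated subjects, two of them spares: Treatment Groups. Planned minimum of ten: Number of Subjects and Rationale for Sample Size; N = 10 in Data Analysis.
- Exposure ends at 8 h: Testing; Criteria for Test End Point.
- Among-subject SD of 2.0 h: the sample-size section, used here only for scale.
- Right-minus-left difference d: not in the documents. The range 0.25 to 1.0 h is an assumption for illustration.

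**The plan's own count.** 12 subjects × 1 arm per product = 12 arms per product, as stated.

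**Can an analysis separate product from side?** Fit one column per subject, one for product and one for side.
- Fixed sides: the product and side columns are identical (correlation 1). The rank is 11 of 12 columns with ten subjects and 13 of 14 with twelve, so one effect cannot be estimated.
- Half the subjects each way: the correlation is 0 and the rank is full (12 of 12; 14 of 14).

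**Size without the 8-hour limit.** Let μA and μB be the side-averaged means, with the right arm at +d/2 and the left at −d/2.
- Fixed: E(mean A) = μA + d/2; E(mean B) = μB − d/2; E(A − B) = μA − μB + d.
- Six each way: E(mean A) = [6(μA + d/2) + 6(μA − d/2)]/12 = μA, and likewise for B, so d cancels.

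| Assumed d (h) | Shift in each mean, d/2 (h) | Shift in A − B, d (h) |
|---|---|---|
| 0.25 | 0.125 | 0.25 |
| 0.5 | 0.25 | 0.5 |
| 1.0 | 0.5 | 1.0 |

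**With the 8-hour limit.** A time that would pass 8 h is recorded as 8 h, so only arms failing earlier show the effect. Assume normal times with SD 2.0 h and a common true mean m. The shift in A − B is then about d × Φ((8 − m)/2).
- m = 8 h: d × Φ(0) = 0.5d.
- m = 10 h: d × Φ(−1) = 0.16d.

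The shift in each product's mean is half of these: 0.25d and 0.08d.

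**Scale.** With SD 2.0 h and n = 10, the 95% t half-width for one product's mean is 2.262 × 2.0/√10 = 1.43 h. Even the uncapped d/2 of 0.125 to 0.5 h lies inside it.

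**Would a coin flip per subject do?** Only on average. An exact split has probability 924/4096 = 22.6% at n = 12 and 252/1024 = 24.6% at n = 10. The leftover shift in A − B has SD d/√n: 0.29d and 0.32d respectively.

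**Drop-outs from a balanced list.** If both of two lost subjects had the same orientation, the split is 6:4. The leftover shift is (6 − 4)/10 × d = 0.2d in A − B, and 0.1d in each mean.

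**The case against.** The strongest reply is that the aliased contrast is not one the study sets out to estimate. The two products are registered separately and analysed separately, 8 hours of protection is expected, and arms that reach 8 h show no side effect at all. The documents offer no evidence that d differs from zero, staff assist insertion to avoid rubbing, and each bare arm must reach 5 landings in 60 seconds before treatment. A fixed side also makes it harder to apply the wrong product.

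Most of this stands and limits the importance of the point. It does not remove it. The landing check is pass/fail on untreated skin, so it does not equalise the arms, and careful insertion does not govern what the arm does between exposures. The guard against swaps is real but small, because wraps already carry the product code.

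Some stronger readings are tempting but unsupported:
- A reader might infer that the fixed side breaks the blind. Staff knowledge is part of the design: "The Study Director and members of the ICR staff will know the actual test articles". Every wrap is labelled with its code, so anyone who sees an arm knows the code under any allocation. Randomising sides changes neither fact.
- A reader might blame cage port or insertion order. No order of arms is stated. Test Cages puts two ports on each of two opposite sides; if cage-mates face each other, which is natural but not stated, the current rule already places A in both halves of the cage.
- A reader might take the full d as the error in each product's time. It is at most d/2, before the 8-hour limit.

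**Conclusion.** The point holds as a cheap improvement to the design, not as a threat to a planned comparison. The complete aliasing of product with side follows from the Protocol's text alone and needs no assumption. Its size does need one. For a side difference of d hours, each product's mean protection time shifts by up to d/2 and an informal A − B comparison by up to d. Under the illustrative normal model these fall to 0.25d and 0.5d when the true mean is 8 h, and to 0.08d and 0.16d when it is 10 h. Since d is unknown and may be negligible, the documents do not support saying that either product's result will be wrong. They do support saying that, if a side effect exists, these data cannot reveal it or correct for it.

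**What to change.** Replace the sentence in Treatment Application with:

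> For each subject the arm receiving A is assigned at random from a prepared list, balanced so that six of the twelve treated subjects receive A on the right arm and six on the left.

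Enter the code for each arm in the COMP row of the raw data collection sheet. The list can be drawn with the lottery already planned.

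Do not give the two subjects sharing a cage opposite orientations. If they face each other, that would put both A arms in one half of the cage and both B arms in the other. One workable layout gives both cage-mates the same orientation, with three of the six cages each way: 3 × 2 = 6 subjects per orientation. The existing practice of treating a pair with one article and then the other still works.

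Cost: a twelve-line list and a one-sentence amendment, with no extra subjects or exposures. The downsides are a small risk of a labelling mix-up and only approximate balance if subjects drop out.

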**MATERIALS**

**TEST ARTICLE NOMENCLATURE**

	Product Name	Specific Gravity	Application Rate	Application/250cm^2
A.	TA# 1001108-030 (A) Currently marketed EPA registered product	0.96	1.67 mg/cm  (EPA Reg. No. 806-29)	417.5 mg.
B.	TA# 1004024-010 (B) Currently marketed EPA registered product	0.96	1.67 mg/cm  (EPA Reg. No. 806-31)	417.5 mg.

**A Material Safety Data Sheet (MSDS) shall be provided for each test, control, and/or reference sample, which will include any hazardous information of the samples. The percentage of all active ingredients and any hazardous constituents must be included in all MSDSs.**

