## 2. Bites from target mosquitoes.

The typical reaction to a bite from a mosquito can vary from person to person. Most people will experience a small area of redness, swelling and itching that usually goes away within 24 hours. In more sensitive individuals, the area of swelling and itching can be much larger and last for several days. In extremely rare cases, a serious reaction to a bite results in swelling of the throat, hives and wheezing. This condition (anaphylaxis) could be life-threatening and requires immediate medical attention.

All subjects known to have severe reactions to mosquito bites will be excluded from this study.

All subjects will be issued latex or vinyl gloves. Only a small portion (250 cm^2) of bare skin on each arm will be exposed. All other parts of the body will be covered with the subject's personal clothing. Immediately upon receiving a FCB on an arm, that arm will be withdrawn from the test and not be exposed to the caged mosquitoes again. Caladryl® or Calamine® lotion and rubbing alcohol will be available for use to mitigate any reaction to mosquito bites.

There will be First Aid qualified staff members on site, and First Aid supplies will be available at the test site at all times. A selected local hospital will receive prior notification of this study and on-site staff will have cell phones to make emergency calls if necessary. In the case of medical emergency, people will be transported to the selected local hospital, St. Agnes Hospital, by either ICR staff or professional ambulance. The hospital is 7 miles from the laboratory and is located at [name], Baltimore, MD. 21229. The telephone number is [contact]. If any test subjects need medical attention, their medical care will be paid by ICR.

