### IX. PHYSICAL DATA

Boiling Point: NA

Vapor Pressure (mm Hg at 20°C): No data

Solubility in Water: Miscible

Viscosity @ 25°C (Cps): NA

pH: 7.5 to 8.5 (liquid component without propellant)

Specific Gravity (H2O=1): 0.87 to 0.93 (liquid component without propellant)

Appearance and Odor: A water-white to straw-colored liquid, lightly fragrances.

---

The information provided in this Material Safety Data Sheet has been compiled from our experience and data with similar, commercially available materials and is believed to be accurate. No guarantee of accuracy is made. It is the user's responsibility to determine the suitability of this information for the adoption of necessary safety precautions.

---

Date Prepared: July 24, 2007

EPA. Reg. No. 806-31

TA# 1004024-010

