## MATERIAL SAFETY DATA SHEET

### IX. PHYSICAL DATA

Boiling Point: Not applicable

Vapor Pressure (mm Hg at 20°C): No data

Solubility in Water: Miscible

pH: 6.75 to 7.75

Specific Gravity (H2O=1): 0.8700 to 0.9300

Viscosity @ 25°C (Cps): Not applicable

Appearance and Odor: Slightly hazy liquid free of foreign matter. with a faint, pleasant odor.

---

The information provided in this Material Safety Data Sheet has been compiled from our experience and data with similar, commercially available materials and is believed to be accurate. No guarantee of accuracy is made. It is the user's responsibility to determine the suitability of this information for the adoption of necessary safety precautions.

---

**Indemnification Agreement  
Between  
Avon Products, Incorporated  
and  
ICR, INC.**

[figure not shown]
Avon Products, Incorporated ("Avon") agrees to hold harmless ICR, Inc. ("ICR") from any claims of injury or illness resulting from the development, evaluation and implementation of Protocol No.G0590607001A117, entitled EVALUATION OF THE EFFICACY OF PERSONAL REPELLENTS AGAINST MOSQUITOES IN THE LABORATORY only under the following circumstances:

[figure not shown]
If any undesirable side effect or reaction occurs following the administration of the test product(s), and if ICR has employed reasonable care in the development of the protocol and has not violated any local, state or federal laws pertaining to the administration of chemical substances, medical devices, drugs or biological agents, including but not limited to the Federal Insecticide, Fungicide, and Rodenticide Act, as amended, and the Federal Food, Drug and Cosmetic Act of 1938, as amended, and the regulations promulgated pursuant thereto, Avon shall indemnify and hold harmless ICR against any and all claims, lawsuits and judgements thereon (including reasonable attorney's fees through the appellate level) which may be brought against it as a result of the development or implementation of the protocol.

In the event any such claim is made or lawsuit is initiated, ICR shall give prompt written notice thereof to Avon, shall permit Avon or its insurance carrier to defend such claim or lawsuit, and shall cooperate fully in any such defense.

ICR, Inc.  
Accepted By:

Avon Products, Incorporated  
Accepted By:

Name:   
[name], BCE

Name: 

Title: Director

Title: Toxicology Manager

Date: 7/25/07

Date: 7/24/07

INDEMNIFICATION AGREEMENT

Between  
Avon Products, Incorporated

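### The protocol names two sources for the amount applied per arm, and its specific gravity of 0.96 lies above the 0.87 to 0.93 on both safety data sheets

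*Protocol*

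**What the plan says.** Three parts of the protocol bear on the amount applied.

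- **Fixed rate.** The Dose paragraph under Experimental Design states "The Standard application rate of 1.67 mg/cm"² and justifies it: "This is the dose currently recommended in the EPA guidelines for mosquito efficacy testing". It adds that the earlier field tests of these two products used the same rate. The Test Article Nomenclature table, which labels each article "Currently marketed EPA registered product", repeats the rate and gives 417.5 mg per 250 cm² for both. It also has a specific gravity column, with 0.96 for both.
- **Another source.** The Treatment Application section, which is the working instruction on the day, names a syringe without a needle as the device and then says: "The amount of test article applied will be determined in the dose range finding".
- **Physical data.** The safety data sheet that lists propellants gives a specific gravity of "0.87 to 0.93 (liquid component without propellant"). The sheet for the second article, which lists no propellant, gives "0.8700 to 0.9300".

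**The concern.** An amount that has already been fixed and justified cannot also be waiting on a later step. Staff who follow Treatment Application are sent to a result that the supplied text does not contain. The contents list, study overview, methods, schedule of events, data sheets and Amendments 1 to 8 do not mention a dose range finding.

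The specific gravity conflict matters because a syringe is a volumetric device. If the mass is converted to a volume with the wrong specific gravity, the delivered mass differs from the reported mass. Protection time is the efficacy measure and can be expected to depend on how much product is on the skin. The protocol also ties its rate to the guideline and to the earlier field tests, and that link needs the delivered rate to be the stated one. The raw data sheet records who applied the formulation but has no field for the amount per arm, so a discrepancy could go unnoticed.

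**Working it through.** **Inputs**

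- Rate: 1.67 mg/cm² (Dose section and Test Article Nomenclature).
- Area per arm: 250 cm² (Test Article Nomenclature, Personnel Preparation, and the section on bites from target mosquitoes).
- Stated mass: 417.5 mg (Test Article Nomenclature).
- Specific gravity: 0.96 (Test Article Nomenclature); 0.87 to 0.93 (both safety sheets, section IX).

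**Step 1: the plan's own figure.** Mass = rate × area = 1.67 × 250 = 417.5 mg. This reproduces the table exactly, so rate and mass agree. The fault lies elsewhere.

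**Step 2: volume implied by the table.** Assume the dose is measured by volume and that a specific gravity of 1 corresponds to 1 mg per microlitre. Volume = mass / specific gravity = 417.5 / 0.96 = 434.9 microlitres.

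**Step 3: what that volume delivers at other specific gravities.** Delivered mass = 434.9 × specific gravity. Rate = mass / 250. Shortfall = 1 − (specific gravity / 0.96).

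| True specific gravity | Delivered mass (mg) | Rate (mg/cm²) | Below stated rate |
|---|---|---|---|
| 0.87 | 378.4 | 1.513 | 9.4% |
| 0.90 | 391.4 | 1.566 | 6.2% |
| 0.93 | 404.5 | 1.618 | 3.1% |
| 0.96 | 417.5 | 1.670 | 0% |

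Seen the other way, 417.5 mg would occupy 417.5 / 0.87 = 479.9 microlitres or 417.5 / 0.93 = 448.9 microlitres.

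**Step 4: the case with no conversion.** If 417.5 mg is weighed out, specific gravity plays no part and the shortfall is 0%.

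**Step 5: could propellant explain the gap?** Perhaps for the first article: its sheet gives the figure for the liquid without propellant, and the table does not say which material its 0.96 and 417.5 mg describe. This does not work for the second article, whose sheet lists no propellant and gives its range without qualification. The page carrying the first article's physical data has the second article's number in its footer. The propellant wording fits the first article and the two ranges are the same, so the comparison is unaffected.

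**The case against.** The strongest reply is that no under-dosing has been shown. The protocol gives the dose as a mass and states no volume. Naming a syringe as the applicator does not say how the dose is measured, and a syringe can be filled by weight. This stands. The specific gravity column, the micropipette among the supplies and the absence of a balance from that list make volumetric dosing plausible, but it remains an inference.

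Second, the safety sheets are weak evidence. Each says that its data come partly from similar commercial materials and that accuracy is not guaranteed. They are not lot measurements, so 0.96 may be the correct figure. This also stands.

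Third, a reader might infer that the results could not support a claim at the stated rate. The documents do not support that. In the scenario computed above every arm receives less than stated, which would tend to shorten protection time and make an 8-hour result conservative. Both articles carry the same 0.96 and the same sheet range, so no bias between them is shown either.

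Fourth, some controls exist. The sponsor must characterise each batch or lot before the experimental start, and sample use forms are archived. Neither is said to cover specific gravity or the amount delivered to each arm.

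Finally, pages were removed before this review, so the dose range finding can be called undescribed only in the supplied text. No competing amount is stated anywhere in that text. None of these replies removes the two contradictions themselves.

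**Conclusion.** Two inconsistencies stand, and neither needs any assumption. The source of the amount per arm is stated in two incompatible ways, and the table's specific gravity lies outside the range on both safety sheets.

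The effect on the delivered rate is conditional: 0% if the dose is weighed or if 0.96 is right, and 3.1% to 9.4% below 1.67 mg/cm² if a volume is set from 0.96 and the sheets are right. The overall range is 0% to 9.4%.

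The documents do not settle which specific gravity is correct or how the dose is measured. They therefore do not support a statement that subjects will be under-dosed, or that a different amount will in fact be used.

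**What to change.** Before the test day:

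- Reconcile the Dose section, the Test Article Nomenclature table and the Treatment Application section so that a single source sets the amount per arm.
- Reconcile the table's specific gravity with both safety sheets, using the sponsor's lot data.
- State whether the mass refers to product with or without propellant, and whether the dose is measured by weight or by volume.
- Record the amount delivered to each arm, on the raw data sheet or on the sample use forms already kept.

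No view is taken on which amount or specific gravity is right. The cost is a short amendment touching a sentence, a table and a recording field, plus a check against the lot characterisation. The sponsor must supply that characterisation in any case, although specific gravity may have to be requested expressly. An amount not recorded on the day may be impossible to recover afterwards.
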